## 2 INTRODUCTION

### 2.1 Background

Catheter-related blood stream infections (CRBSI) are bacterial infections that originate within a vascular access device (VAD). The International Society for Infectious Diseases report that CRBSIs account for 11% of all healthcare-associated infections and have an estimated attributable mortality rate between 12-25% (Lutwick and Bearman, 2019).

Introduction of bacteria into the bloodstream via the VAD can come from several sources, including contamination of the device prior to insertion, skin organisms, contamination of the infusate, and contamination of the catheter hub (Gahlot, 2014). There are multiple recommendations for CRBSI prevention that targets each of these potential origin points. For needleless connectors, the guidelines for the Prevention of Intravascular CRBSIs considers scrubbing the access port of needleless connectors with an appropriate antiseptic (including 70% IPA) a Category 1A recommendation (O’Grady et al, 2017). Standards of clinical practice published by Society for Healthcare Epidemiology of America (SHEA) and Infusion Nurses Society (INS) have included disinfection caps in their recommendations (Marschall et al, 2014; Infusion Nurses Society, 2021).

Alcohol-impregnated disinfectant caps were developed to simplify the disinfection process through passive disinfection. Furthermore, disinfectant caps act as a physical barrier between line accesses (Marschall 2014, Infusion Nurses Society, 2021). The BD PureHub™ disinfecting cap was designed for compatibility with market-leading needle-free connectors prior to access and maintains a physical barrier to contamination for up to seven days. The BD PureHub™ disinfecting cap disinfects with a sterilized 70% IPA solution, providing a > 4-log (99.99%) reduction in bacteria within 1 minute of application.

### 2.2 Rationale

This study is designed to provide data utilizing the BD PureHub™ Disinfecting Cap for the purpose of providing clinical data required under EU regulation 2017/745.

### 2.3 Risk/Benefit Assessment

The BD PureHub™ Disinfecting Cap has been on the market in Europe since 2018 and as of July 2020, PureHub™ has been used in 122 institutions in EU and 131 institutions in US with more than 21.9 million units sold.

More detailed information about the known and expected benefits and risks and reasonably expected adverse events of BD the PureHub™ Disinfecting Cap may be found in the Instructions for Use (IFU).

#### 2.3.1 Risk Assessment

Potential risks for the BD PureHub™ Disinfecting Cap devices are based on items noted in the Instructions for Use and are not unique to this study.

Potential Risk of Clinical Significance	Summary of Data/Rationale for Risk	Mitigation Strategy
		Study Intervention (s)
The BD PureHub™ Disinfecting Cap has a potential for trace amounts of IPA to ingress from the disinfecting cap into the fluid path of the infusion therapy system.	
A review of literature showed positive outcomes for the application as intended for the use of the BD PureHub™ Disinfecting Cap. A general patient benefit has been identified within the literature. However, one in-vitro study on another disinfecting cap found that use caused a change in the appearance of some E valves, and also allowed significant amounts of IPA to be injected.
 
However, an assessment considering BD PureHub™ Disinfecting Cap found that the estimated ingress dose amount of BD PureHub™ disinfecting cap was determined to be below the BD derived acceptable exposure limit of IPA secondary to potential ingress.
	A caution statement “The safety of 70% Isopropyl Alcohol caps has not yet been directly established in clinical use scenarios with neonates” has been added to the BD PureHub™ Disinfecting Caps IFU. A warning statement “Keep out of reach of children. In case of accidental ingestion, seek medical help or consult a poison control center immediately”, is included in the BD PureHub™ Disinfecting Caps IFU.
Potential choking hazard for the pediatric population	
The literature also identified disinfectant caps as esophageal foreign bodies in pediatric patients, suggesting that they should be used with caution in this patient population given their potential to become ingested. One event like this was also identified in the database analysis of Clinical Experience.
 
A potential for a choking hazard exists with a pediatric patient if the user does not apply the cap properly and the cap inadvertently falls off during unsupervised use or is not disposed of properly. Choking hazards are prevalent and always a risk with pediatric patients. The benefits of the disinfecting cap currently outweigh the risk of potential for choking. The risk has been assessed as mitigated and has been determined to be acceptable.
	The IFU instructs the user of proper application of the disinfecting cap, and to discard after use. A warning statement, “Potential choking hazard”, is included in the BD PureHub™ Disinfecting Cap IFU.

Potential Risk of Clinical Significance	Summary of Data/Rationale for Risk	Mitigation Strategy
Study Intervention (s)		
Process considerations that could lead to particulate within sponge assembly	These are identified potential process considerations	The IFU instructs clinicians that: “After removing the foil film, visually inspect the contents of the cap and do not use if it appears dry or contains particulate matter.”
Process considerations that could lead to a dry sponge or insufficient IPA amount that may lead to ineffective disinfection.	These are identified potential process considerations	The IFU instructs clinicians that: “After removing the foil film, visually inspect the contents of the cap and do not use if it appears dry or contains particulate matter.”
Study Procedures		
No study-specific risks identified		
Other		
Not applicable		

### 2.3.2 Benefit Assessment

There is no direct benefit for study participation for an individual patient, however the clinical benefits for the BD PureHub™ Disinfecting Cap are as follows:

- a. Easy to use disinfecting device for needle-free connectors.
- b. Easy to use device to act as a physical barrier on needle-free connectors between line accesses.
- c. Demonstrated in a laboratory a >4 log (99.99%) reduction on common causative agents in CRBSI including: *Staphylococcus aureus*, *Staphylococcus epidermidis*, *Pseudomonas aeruginosa*, *Escherichia coli*, *Candida glabrata*, *Candida albicans*, *Acinetobacter baumannii*.
- d. The BD PureHub™ Disinfecting Cap complies with the Infusion Nursing Society (2021) recommendation to perform passive disinfection on needle-free connectors by applying a cap or covering containing a disinfectant agent (e.g., 70% isopropyl alcohol, iodinated alcohol) to create a physical barrier to contamination between use.

### 2.3.3 Overall Benefit: Risk Conclusion

The BD PureHub™ Disinfecting Cap will be used by trained individuals as intended as part of this study on any patient population with consideration given to the procedure being performed and the disease state of the patient. There is no anticipated additional risk associated with the device use or any study procedure due to participation in this study compared to any BD PureHub™ Disinfecting Cap use as part of standard medical care.

## 3 OBJECTIVES AND ENDPOINTS

Objectives	Endpoints
Primary Performance Objective	
To assess the rate of select performance measures of the BD PureHub™ Disinfecting Caps on swabbable needle-free connectors when used in a clinical environment.	

Attachment success rate of the BD PureHub™ Disinfecting Caps to a needle-free connector (successful attachment/total number of attachments)

Removal success rate of the BD PureHub™ Disinfecting Caps to a needle-free connector (successful removal/ total number of intended removals)

Primary Safety Objective	

Rate of device-related adverse events

Informational Objective	

The number of BD PureHub™ Disinfecting Caps used per day/per study participant

To summarize the purposes for removal of the BD PureHub™ Disinfecting Cap from the needle-free connector	

The purpose for each intended removal of the BD PureHub™ Disinfecting Cap from the needle-free connector

To summarize the incidence of blood stream infection	

Incidence of central line associated bloodstream infection (CLABSI)

Incidence of bloodstream infections

## 4 STUDY DESIGN

### 4.1 Overall Design

This is a multi-center, single-arm, prospective post-market study that will enroll up to 175 participants in order to have 150 evaluable participants who have vascular access devices as part of their routine medical care. Data related to the safety and performance of the BD PureHub™ Disinfecting Cap will be captured when used as intended.

Participants will be screened against eligibility criteria and will be considered enrolled once the informed consent document is signed. Each study participant will have a BD PureHub™ Disinfecting Cap attached to each eligible needle-free connector to one or more VADs by a clinician. Clinicians will then be advised to place subsequent BD PureHub™ Disinfecting Caps as per the Instructions for Use through the course of the participant's IV therapy. During this time, attachment and removal success will be captured, as well as any device-related adverse events (AEs).

Participants will be followed from the time of enrollment until one week post VAD therapy, department/hospital discharge or 45 days post enrollment date, whichever comes first. Participants, with a VAD in place, who will be discharged from the hospital, but return regularly for catheter access to the site will remain in the study, either until the 45 days are reached or the VAD therapy is ended. If the catheter access will not be performed at the clinical trial site, the participant cannot continue in the study.

### 4.2 Scientific Rationale for Study Design

This study is designed to collect clinical data on the performance of the BD PureHub™ Disinfecting Cap. The usage of the BD PureHub™ Disinfecting Cap according to its intended use will ensure that study activities have no direct impact on the endpoints being assessed and that they represent outcomes typically associated with intended medical use of the study device in clinical practice.

#### 4.2.1 Participant Input into Design

Not applicable.

### 4.3 End of Study Definition

A participant is considered to have completed the study when one of the following conditions are met, whichever is the earliest.:

- upon one week post VAD therapy (after the last VAD is removed),
- at department discharge provided the clinical investigation team cannot follow-up the participant on another ward for study purposes,
- at hospital discharge provided participant, if VAD is still placed, will not return for catheter access to the site or,
- 45 days from enrollment

If a participant has more than one (1) VAD with eligible needle-free connectors at study start, data will be collected on each VAD and the end of study time point occurs when the last VAD is removed. If an additional VAD is placed at a later time point, or if one of these VADs is replaced, then the new VAD is excluded from the study.

The end of the study is defined as the date of the last study assessment of the last participant in the study.

## 5 STUDY POPULATION

### 5.1 Inclusion Criteria

In order to be eligible to participate in this study, an individual of any age or gender, must meet all of the following criteria:

1. Has an eligible vascular access device in situ or will have one placed with needle-free connectors  
Note: This covers all needle-free devices, including central venous catheters, peripheral IV catheters and arterial VADs
2. Is expected to receive VAD therapy for a minimum of 3 days
3. Is expected to be available for regular observation from consent until end of study.
4. Able and willing to provide informed consent or legal authorized representative (LAR)\* authorized to give consent on behalf of the participant.

\*LAR not applicable for AT01

### 5.2 Exclusion Criteria

Participants are excluded from the study if any of the following criteria apply:

1. BD PureHub™ Disinfecting Cap or any other disinfecting cap in place for more than twelve (12) hours (>12 hours) prior to study participation
2. Presence of any infection, bacteremia, or septicemia is known or suspected
3. Any condition which, in the opinion of the Investigator, precludes the participant from participation in this study

### 5.3 Lifestyle Considerations

Not applicable.

### 5.4 Screen Failures

Screen failures are not anticipated due to the non-investigational nature of the study.

### 5.5 Vulnerable Population

As the instruction for use of the BD PureHub™ Disinfecting Caps does not foresee any limitations in terms of subject age or status and the study aims to collect data on clinical use, the study will also consider participants under 18 years of age, or participants requiring a LAR. In addition, pregnant and breastfeeding subjects are not excluded from study participation. As the study device will be used as intended, this population is considered to be not exposed to any additional risk due to study participation.

Some participating clinical sites may decide to not include vulnerable subjects as per their hospital policy or may not include minors as the participating department treats only adults.

## 6 STUDY INTERVENTION

### 6.1 Investigational/Test Device

BD PureHub™ Disinfecting Caps are intended to be used as a disinfecting device for swabbable needle-free luer connectors prior to access and to act as a physical barrier between line accesses. It is comprised of a threaded plastic cap containing a porous pad pre-saturated with 70% IPA, and sealed with a multilayer foil film. The BD PureHub™ Disinfecting Cap will disinfect the needle-free luer connector one (1) minute after application and act as a physical barrier for up to seven (7) days, if not removed. Proper application and removal of the device is detailed in the IFU. This product is not made with natural rubber latex or plasticizer Diethylhexyl Phthalate (DEHP). A picture of the device is provided below.

Figure 1 Example of disinfecting cap (BD PureHub™ disinfecting cap)

### 6.2 Control Device/Standard of Care

Not applicable; this is a single-arm study.

### 6.3 Ancillary Devices/Products

Ancillary devices will include the participant's VAD, eligible needle-free luer connectors, intravenous tubing, and dressings, or any other material associated with the participant venous access. These products will be used as part of the standard of care of each site. Selected information regarding these devices will be collected (See Section 7.7). The use of other disinfecting caps than the PureHub™ disinfecting cap is not allowed.

### 6.4 Device Labeling

This study will utilize marketed product. As such, no special labelling is required. However, to ensure that the BD PureHub™ disinfecting cap will be used at the study sites only on behalf of the study, the device packaging will be labeled as "For clinical trial use only".

## 6.5 Treatment Allocation and Measures to Minimize Bias

This is a post-market clinical follow up study in which the BD PureHub™ disinfecting cap is used as intended. The choice of using the cap is left to the discretion of the clinician.

# 7 STUDY PROCEDURES AND ASSESSMENTS

- Study activities and their timing are summarized in the Schedule of Activities (Table 1)
- Adherence to the study design requirements, is essential and required for study conduct.
- All screening evaluations must be completed and reviewed to confirm that potential participants meet all eligibility criteria. The investigator will maintain a screening log to record details of all participants screened and to confirm eligibility or record reasons for screening failure, as applicable.

### 7.1 Study duration

The study participation per participant will last 45 days at maximum, the overall conduct of the study is expected to last approximately 14-15 months from first participant enrolled up to last participant having last visit, which is projected for ~ Q2 2023. The anticipated enrollment period is 13 months.

### 7.2 Screening and Enrollment

After screening against inclusion/exclusion criteria, potential participants will be provided with detailed information about the study. For details on the Informed Consent process, please refer to section 14.2. A participant will be considered enrolled once informed consent (or assent as applicable) is signed. Enrolled patients will be assigned a unique participant number.

### 7.3 Medical History / Baseline Assessments

Participant baseline and demographic information will be documented, including, but not limited to age, sex assigned at birth, primary diagnosis, and medical history. Information on the participants vascular access device, including but not limited to:

- Type of VADs to be assessed per study participant
- Per VAD the following information will also be collected:
  - Date of insertion
  - Date of removal
  - VAD placement site location
  - Number of lumens
  - Type of dressing/securement
  - Type and number of needle-free connector(s),
  - Type and number of intravenous tubing/ extension set(s)
  - Type and number of other add-on devices i.e. valves, stop cocks

## 7.4 Device Use

Each study participant will have a BD PureHub™ Disinfecting Cap attached to each eligible needle-free connector by a clinician. “Eligible” needle-free connector will be defined as a swabbable needle-free connector not already in use and is reasonably able to be accessed by a clinician.

Clinicians should place subsequent BD PureHub™ Disinfecting Caps as per the Instructions for Use. Lot numbers of the PureHub™ devices will be documented in the eCRF.

Clinicians will be advised to follow the respective unit protocol for disinfection of needle-free luer connectors prior to initial access.

## 7.5 Efficacy (Performance) Assessment

Clinicians will be requested to document the following with each use of the BD PureHub™ Disinfecting Cap:

- Attachment success: The clinician will document if able to successfully attach the BD PureHub™ Disinfecting Cap to each of the applicable needle-free connectors securely. (Documenting either “Yes” or “No”).
  - An *attachment* is defined as the process of placing a PureHub™ Disinfecting Cap on an eligible needle-free connector.
  - If the clinician can successfully attach the first BD PureHub™ Disinfecting Cap, they should document “Yes” as this would be an attachment success. Attachment success means the cap is securely attached to the needle-free connector and that the needle-free luer is connected.
  - If the clinician is unable to successfully attach the cap to the needle-free connector, they should use a new subsequent BD PureHub™ Disinfecting Cap. The answer to attachment success would be “No” as more than one cap was needed to reach attachment success. The number of subsequent caps needed to achieve a successful attachment during this procedure need to be documented.

If the clinician is unable to attach the cap to the needle-free connector with any subsequent caps, they should document the number of subsequent caps used and document “Unable to attach.”

- Removal success: The clinician will document if able to successfully remove the BD PureHub™ Disinfecting Cap from the needle-free connector (Yes/No).
  - An *intended removal* is defined as the process of removing a successfully attached PureHub™ Disinfecting Cap from an eligible needle-free connector for the purpose of access to the needle-free connector or to replace with a new PureHub™ Disinfecting Cap.

If the clinician can remove the PureHub™ Disinfecting Cap from the needle-free connector, they should document “Yes” as this would be a removal success.

If the clinician cannot remove the PureHub™ Disinfecting Cap from the needle-free connector, they should document “No”.

## 7.6 Safety Assessments

Device-related AEs and device deficiencies will be captured as they occur until the participant concluded his/her participation to the study. Details about AEs are provided in Section 9.

## 7.7 Informational Assessments

The following data may also be collected for informational purposes only:

- Participant in-hospital location: Main department/ward, date of hospitalization, if applicable: any participant transfer in the hospital provided participant is still followed up by the clinical investigation team: date of move to another department/ward, name of new department/ward
- Vascular access device details used in conjunction with the BD PureHub™ Disinfecting Cap. In addition to the VAD information to be collected as referenced in section 7.3 , the following information will be documented throughout the study:
  - Per catheter:
    - Type of dressing
    - Dressing changes
    - Needle-free connector changes
    - Daily assessment of any change to type and number of intravenous tubing/extension set(s)
    - Daily assessment of any change to type and number of other add-on devices i.e. valves, stop cocks
  - Current catheter care practice
- The number of BD PureHub™ Disinfecting Caps used per day/per study participant
- The primary reason for each intended removal of the BD PureHub™ Disinfecting Cap removal.
- Incidence of bloodstream infection, including CLABSI will be documented.

# 8 PARTICIPANT DISCONTINUATION/WITHDRAWAL

## 8.1 Discontinuation/Withdrawal

- A participant may withdraw from the study at any time at his/her own request or may be withdrawn at any time at the discretion of the investigator or sponsor for safety, behavioral, compliance, or administrative reasons. This is expected to be uncommon.
- At the time of discontinuing from the study, no further data will be collected for the participant.

- If the participant withdraws consent for disclosure of future information, the sponsor may retain and continue to use any data collected before such a withdrawal of consent.
- Participants who withdraw or discontinue the study early may be replaced.

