# 9 ADVERSE EVENTS AND DEVICE DEFICIENCIES

## 9.1 Definitions of Events

### 9.1.1 Adverse Events (AEs)

An AE is defined as any untoward medical occurrence, unintended disease or injury, or untoward clinical signs (including abnormal laboratory findings) in participants, users or other persons, whether or not related to study device or procedure and whether anticipated or unanticipated [ISO14155:2020].

In this study, AE collection will be limited to those events judged to be related or likely related to the BD PureHub™ Disinfecting Cap and any events of bloodstream infection, including CLABSI (as defined in the List of Abbreviations).

Pre-existing conditions should be considered as part of the participant's medical history and should not be reported as an AE unless there is a substantial increase in severity or frequency of the condition, which has not been attributed to natural history. Likewise, planned hospital visits and/or hospital stays should not be considered as adverse events. Exacerbation of an existing condition should be reported as an AE if the event meets the protocol definition of an AE.

The clinical course of the event will be followed according to accepted standards of medical practice until the event resolves, stabilizes, or in the opinion of the Investigator, is no longer considered clinically significant. The Investigator must supply the Sponsor with information concerning the follow up and/or resolution of the AE.

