5.3 Informational Endpoint(s)

The informational endpoints are:

- The number of BD PureHub™ Disinfecting Caps used per day/per study participant
- The purposes for each intended removal of the BD PureHub™ Disinfecting Cap from the needle free connector
- Incidence of central line associated bloodstream infection (CLABSI)
- Incidence of bloodstream infections

The calculation of number of PureHub caps used per day will be total number of caps used (including the ones attempted but didn’t attach) divided by number of days participants were in VAD therapy. If multiple VADs were removed, number of days will be last VAD removal date – PureHub initial placement date. If at least one VAD is not removed, the number of days will be the minimum of study duration (participant end of study date – PureHub initial placement date) and 45 days. The number of caps used will be from the following CRF pages:

- PureHub Initial Placement page, Number of caps used
- PureHub Maintenance page, Number of caps used

The purposes of removal of the BD PureHub™ Disinfecting Cap are identified on “PureHub Maintenance” log in response to “Removal reason” question. The percentage of each response will be provided, and the denominator will be the total number of intended removals.

Incidence of bloodstream infections can be identified on the CRF “Adverse Events” log form. If response to “In case of bloodstream infection, how was it confirmed” is not “Blood Stream Infection Not Present”, then subject had a bloodstream infection.

Central line associated bloodstream infection can be identified if the response to “Is the bloodstream infection central-line associated” is “Yes” on the CRF “Adverse Events” log form.

The analysis will be performed on the evaluable population. Descriptive statistics for the informational endpoints will be provided. Summary statistics for categorical variables will include frequency counts and percentages and for continuous variables will include mean, standard deviation, minimum, median, and maximum.

6 Summary of General Study Data

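### Protocol 8.1 ends all data collection at any discontinuation, in conflict with the AE follow-up duty in 9.1.1; later safety and infection outcomes go unrecorded while the SAP counts those participants as event-free

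*Protocol*

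**What the plan says.** Protocol 8.1 covers participants who leave at their own request and those who "may be withdrawn at any time at the discretion of the investigator or sponsor for safety, behavioral, compliance, or administrative reasons". One rule then applies to all of them: "At the time of discontinuing from the study, no further data will be collected for the participant". Withdrawal of consent is a separate bullet: "If the participant withdraws consent for disclosure of future information, the sponsor may retain and continue to use any data collected before" that withdrawal. The section adds "This is expected to be uncommon" and "Participants who withdraw or discontinue the study early may be replaced", and gives no rate.

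Protocol 7.6 captures device-related AEs and device deficiencies until the participant's participation ends.

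Protocol 9.1.1 limits AE collection to events related or likely related to the cap and any bloodstream infection. For these, "The clinical course of the event will be followed according to accepted standards of medical practice until the event resolves, stabilizes" or is no longer clinically significant in the investigator's opinion. It continues: "The Investigator must supply the Sponsor with information concerning the follow up and/or resolution of the AE". No exception is made for discontinued participants.

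SAP 5.2 divides participants with a device-related AE by the enrolled population. SAP 5.3 analyses bloodstream infection and CLABSI in the evaluable population and takes both from one source: "Incidence of bloodstream infections can be identified on the CRF" AE log form. SAP 6.1 tabulates withdrawals with reasons. The SAP has no rule for participants whose safety follow-up was cut short.

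**The concern.** A site with an open AE at discontinuation cannot follow 8.1 and 9.1.1 together. Because 8.1 handles withdrawal of consent for future information in its own bullet, the general stop is not needed to respect consent. It also reaches participants who never objected to further data collection.

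The primary safety endpoint is a crude proportion, and the infection endpoints are incidences. A participant whose observation ends early with no event recorded enters both as event-free. If the reason for leaving is safety, the truncation may be related to the outcome. The sample size sections consider AE rates of 1% and 2% per participant, so results may turn on one or two events. The later seriousness and outcome of open events would also be incomplete in the AE summaries planned in SAP section 7.

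**Working it through.** **1. The plan's own safety figures.** Protocol 10.2 and SAP 2.4 give the chance of seeing at least one event in 150 participants as 1 − (1 − p)^150.
- p = 0.01: 1 − 0.99^150 = 77.9% (stated 78%).
- p = 0.02: 1 − 0.98^150 = 95.2% (stated 95%).

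Both reproduce. No stated number is in dispute.

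**2. What each rule does with an event, by timing.**

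| Situation | 8.1 and 7.6 as written | 9.1.1 as written | Effect on the rates |
|---|---|---|---|
| AE judged related or likely related by the day of discontinuation | Recorded under 7.6 | Recorded | Counts in the SAP 5.2 numerator |
| Later course, seriousness and outcome of that AE | Not collected | Must be followed and reported | Primary rate unchanged; AE summaries incomplete |
| Sign present at discontinuation, relatedness or infection confirmed only later | Not collected | Must be followed if already an AE; otherwise unclear | May be missed |
| New device-related AE or bloodstream infection after discontinuation, within the planned window | Not collected | Not clearly covered | Missed; participant counted as event-free |

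The second row is the direct contradiction. The last two rows are where the rates can be biased. Giving 9.1.1 precedence would not close the last row, because its follow-up duty attaches to an existing event.

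**3. Denominators.** SAP 5.2 uses the enrolled population (up to 175, Protocol 4.1). SAP 5.3 uses the evaluable population (target 150). A discontinued participant stays in the first, and in the second if a cap was applied. A missed event therefore lowers the numerator and leaves the denominator unchanged, so the error in the crude rate can only be downward.

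**4. Sensitivity of the primary safety result to single events (illustration).** The Clopper-Pearson 95% upper limit is the 0.975 quantile of Beta(x + 1, n − x). With n = 175:
- x = 0: rate 0%, upper limit 2.1%.
- x = 1: 1/175 = 0.57%, upper limit 3.1%.
- x = 2: 2/175 = 1.14%, upper limit 4.1%.

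**5. How many events might be missed (assumptions, not document figures).** Let a share f of 175 discontinue, each with event risk p, and suppose every one of their events is missed. The expected number missed is 175 × f × p.
- f = 3%, p = 1%: 175 × 0.03 × 0.01 = 0.05.
- f = 10%, p = 2%: 175 × 0.10 × 0.02 = 0.35.

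At these values of p this overstates the loss, since events before discontinuation are recorded. A higher risk among discontinuers would raise it, but the documents give no basis for a figure.

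**6. Loss of detection.** If d of 150 were wholly unobserved, the chance of seeing at least one event is 1 − (1 − p)^(150 − d). For d = 8 it is 76.0% (p = 1%) and 94.3% (p = 2%), against 77.9% and 95.2% at d = 0. The loss is small.

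**The case against.** The strongest defence is that 9.1.1 is the specific rule and 8.1 the general one, so AE follow-up survives discontinuation. Protocol 9.4 also requires serious events to be reported within three working days of awareness, with no exception for discontinued participants, and 9.7 provides for assessment of serious health threats. This has force. A reader might infer that open events would go unreported to the sponsor; the documents do not establish that. But no precedence is stated, and 7.6 and footnote 4 of Table 1 tie safety assessment to continued participation.

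A reader might also infer that an AE that triggers a safety discontinuation vanishes from the primary safety rate. It does not. If judged related or likely related by then, it is recorded under 7.6 and counts.

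Three further points stand. Exposure to study caps would be expected to end at discontinuation, since they are labelled for trial use only, so new device-related AEs would mostly be carry-over. Follow-up also ends at discharge by design, so unobserved later events are counted as none for some completers too. The infection endpoints are informational, and SAP 2.8 sets no acceptance criteria, so no pass/fail result changes. These points limit the size of the problem and leave the contradiction in place.

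**Conclusion.** The concern holds as a conflict between stated rules with a limited effect on the analysis. Protocol 8.1 and 7.6 end collection at any discontinuation, 9.1.1 requires follow-up and reporting, and nothing reconciles them. At risk are the later course, seriousness and outcome of open events, relatedness or infection confirmed only afterwards, and new device-related AEs or bloodstream infections within the planned follow-up.

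Any bias in the SAP 5.2 and 5.3 rates is downward. Its size cannot be computed, because the protocol says only that withdrawal should be uncommon. Under the assumed 3% to 10% discontinuation and 1% to 2% risk, fewer than one event would be expected to be missed, so it is probably small. The upper limits for 0, 1 and 2 events in 175 show how far one or two events would move the result; they do not predict that events will be lost. Confidence is high for the conflict in the text and low for any figure for its effect. A correction is worth making because it concerns the primary safety endpoint and is cheap.

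**What to change.** Reconcile Protocol 7.6, 8.1 and 9.1.1 together; changing only 8.1 and 9.1.1 would leave 7.6 in conflict.
- Stop all data collection only when consent to further data collection is withdrawn. Ask participants who leave at their own request whether safety data may still be collected, and record the answer.
- For any other discontinuation, stop only the cap-use records. Continue recording device-related AEs and bloodstream infections to the endpoint already defined in 4.3.
- State in 9.1.1 that its existing follow-up duty applies to AEs open at discontinuation.
- In the SAP, report the number of participants with incomplete safety follow-up beside the safety and infection rates.

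The cost is a protocol amendment with ethics committee notification or approval, possible consent-form wording, and a few extra safety entries. No new type of assessment is needed. If an amendment comes too late, the SAP line and a clarification to sites would still help.
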